7.2.2.1. Intercurrent events and handling of missing data

The intercurrent events mentioned in Section 1.1.2. along with the corresponding strategies will be considered during this analysis.

- For treatment discontinuation due to any reason:
Subjects' data available up to the withdrawal will be included in the analysis. If a subject withdraws consent during a period, the missing data post withdrawal will not be imputed.
- For Subject use concomitant/prohibited medication:
The subject data post consumption of concomitant/prohibited medications (intercurrent event) will be analyzed as collected.

If multiple intercurrent events are observed, then the data will be handled using more than one strategy as described in Section 1.1.2. and interpretations of the results will be made accordingly.

Graphical presentations will be provided, if appropriate. All data will be listed. Details of the planned displays are provided in the Output Programming Specification (OPS) document. Data Displays will be based on GSK Data Standards and statistical principles.

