4.4. Scientific Rationale for Study Design

This study will be the first administration of GSK3494245 in human participants. The primary purpose of the current study is to characterise the safety and tolerability of GSK3494245 in healthy participants within a controlled PK range. The study will additionally seek to understand the secondary and exploratory endpoints. Specific scientific considerations which contribute to the study design include:

- In the SAD part, this study employs a randomised sequential crossover design to allow for dose comparison between and within participants at different dose levels. In addition, this design minimises participant numbers across the SAD part of the study and is appropriate given the short-estimated half-life of GSK3494245 (approximately 4 h), which enables a short washout period.
- Furthermore, a food-effect evaluation is planned to support progression into patient studies. An assessment of food effect on the exposure to GSK3494245 will be incorporated into the SAD part of the study. Preliminary assessment of food-effect hinted a marginal decrease in the drug exposure which could possibly be attributed to high stomach solubility in the fasted acidic stomach that is not present in the fed state due to a higher pH. In the presence of food, the exposure may be slightly lower or the same in terms of overall trend. Please see Section 9 for further details on how sample size was determined for the food effect cohort. The exact sample size for the evaluation of the food effect will be determined based on the variability of the AUC and C_{\max} observed in Cohorts 1 and 2. Up to a maximum of 16 participants will be recruited to allow for 12 evaluable participants, however as few as 10 evaluable participants may be required, in which case the number of participants recruited could be slightly lower. The

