6.5. Concomitant Therapy

Any medication or vaccine (including over-the-counter or prescription medicines, recreational drugs, vitamins, and/or herbal supplements) that the participant is receiving at the time of enrollment or receives during the study must be recorded along with:

- reason for use
- dates of administration including start and end dates
- dosage information including dose and frequency

The Medical Monitor should be contacted if there are any questions regarding concomitant or prior therapy.

Participants must abstain from taking prescription or non-prescription drugs (including vitamins, recreational drugs and dietary or herbal supplements, NSAIDs, PPIs and anti-H2 antagonists) within 7 days (or 14 days if the drug is a potential enzyme inducer) or 5 half-lives (whichever is longer) before the start of study treatment until completion of the follow-up visit, unless, in the opinion of the investigator and sponsor, the medication will not interfere with the study.

Paracetamol at doses of ≤ 2 grams/day is permitted for use any time during the study. Other concomitant medication, or paracetamol at doses of >2 g, may be considered on a case-by-case basis by the investigator, in consultation with the Medical Monitor if required.

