7.1.8. Individual Safety Stopping / Withdrawal Criteria

- If a participant experiences a serious or severe clinically significant AE that in the clinical judgement of the Investigator is possibly, probably or definitely related to investigational product. It is **recommended** that the medical monitor is consulted before a decision is made.
- The participant initiates treatment with any prohibited medications.
- If any of renal, liver chemistry, ECG and telemetry, olfactory or mitochondrial toxicity stopping criteria are met (see Section 7.1.3, Section 7.1.4, Section 7.1.5, Section 7.1.6 and Section 7.1.7).
- The participant develops stomach erosion as confirmed clinically and following a gastro enterology specialist's opinion for further management, and endoscopy (if required).
- If a participant develops COVID-19 like symptoms during the study the following actions should be taken:
 - Participants who develop a high clinical index of suspicion for COVID-19 disease should be isolated and tested for COVID-19 in accordance with site procedures.
 - Assessments should be continued as per the protocol during this period; withdrawal of participants from the study will be at the discretion of the Principal Investigator but should first be discussed and agreed with the Medical Monitor.

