SAD Part: Derived PK parameters will be collected for GSK3494245 following single dose (fasted and fed) including area under the plasma drug concentration versus time curve (AUC(0-t) AUC (0- ∞)), maximum observed plasma drug concentration (C_{max}), time to maximum observed plasma drug concentration (T_{max}), and apparent terminal half-life (t_{1/2}) as data allow.

MAD part: as appropriate:

 - Day 1 AUC(0-t), AUC (0- ∞), AUC(0-tau), C_{max}, T_{max}, t_{1/2}
 - Day 4-7 morning trough plasma concentration (C_{tau})
 - Day 7 AUC(0-t), AUC(0-tau), C_{max}, T_{max}, t_{1/2}, CL_{ss}
 - Additionally, for TID regimen if conducted): Day 6 evening dose AUC(0-t), AUC(0-tau), C_{max}, T_{max},
- **Population Level Summary measure:**

Descriptive statistics for log transformed data and untransformed data will be presented with mean, median, standard deviation, minimum and maximum.

- **Intercurrent events:**
 - a) Treatment discontinuation due to any reasons– While on treatment policy strategy will be used.
 - b) Use of concomitant/prohibited medication – Treatment policy strategy will be used.
- **Rationale for Estimand:**
 - a) Interest lies in the treatment effect prior to the withdrawal- all available data up until the withdrawal of the consent will be reported.
 - b) Interest lies in the overall treatment effect- The data post consumption of concomitant/prohibited medications (intercurrent event) will be analyzed as collected.

Secondary Estimands 2:

The clinical question of interest for the secondary objective is:

To examine dose proportionality for the following single doses of GSK3494245 for fasted and fed cohorts separately.

The estimand is described by the following attributes:

- **Population:** Healthy participants of age 18 to ≤ 55 years.
- **Treatment condition:**
 - The SAD part will consist of a single-dose escalation phase in up to 3 cohorts and a food effect cohort. On completion of Cohort 3, Cohort 3a will assess single ascending doses of GSK3494245 taken with food.
- **Endpoint:**

Area under the plasma GSK3494245 concentration by time curve AUC (0- ∞),
Maximum observed plasma drug concentration (C_{max}).
- **Population Level Summary measure:**

Estimate of slope and corresponding 90% Confidence Interval (CI).

- **Intercurrent events:**
 - a) Treatment discontinuation due to any reasons–Hypothetical strategy will be used.
 - b) Use of concomitant/prohibited medication – Treatment policy strategy will be used.
- **Rationale for Estimand:**

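### The SAP keeps PK profiles affected by prohibited medication as collected, does not separate them from profiles with permitted medication, and gives no precedence when discontinuation also occurs

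*SAP*

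**What the plan says.** SAP 1.1.2 has three secondary PK estimands: PK profile, dose proportionality, and accumulation with time invariance and steady state. Each one says: "Use of concomitant/prohibited medication – Treatment policy strategy will be used". The rationale given is interest in the treatment's overall effect. Sections 7.1.2.1, 7.2.2.1, 7.3.2.1, 7.4.2.1, 7.5.1.1 and 7.6.2.1 carry this into the analyses; the food-effect section reads "The subject data post consumption of concomitant/prohibited medications (intercurrent event) will be analyzed as collected".

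The PK analysis set (SAP 3) needs only one non-missing PK assessment. The discretion to drop data in SAP 7.1.1 concerns partial concentration data, the terminal-phase fit and the extrapolated area. It does not cover medication. The SAP describes no sensitivity analysis without affected profiles.

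Protocol 6.5 requires participants to abstain from drugs that include "dietary or herbal supplements, NSAIDs, PPIs and anti-H2 antagonists". The window is 7 days, 14 days for a potential enzyme inducer, or 5 half-lives, whichever is longer. Paracetamol up to 2 g/day is permitted, and other drugs may be allowed case by case. Protocol 7.1.8 lists as an individual stopping or withdrawal criterion: "The participant initiates treatment with any prohibited medications". Under 7.1, discontinuation is permanent.

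Protocol 4.4 suggests, tentatively, that lower fed exposure could come from "high stomach solubility in the fasted acidic stomach that is not present in the fed state due to a higher pH".

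For dose proportionality and for accumulation, time invariance and steady state, the SAP says: "Treatment discontinuation due to any reasons–Hypothetical strategy will be used". For the PK profile it uses a while-on-treatment strategy. When several intercurrent events occur, "then the data will be handled using more than one strategy as described in Section 1.1.2".

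**The concern.** A fed:fasted ratio, a dose slope and an accumulation ratio describe the drug's own kinetics. A profile taken under an acid reducer or an enzyme inducer measures drug plus interaction. Keeping it is a reasonable answer to a question about overall effect in use, but these analyses do not ask that question.

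The single category also treats a dose of paracetamol within the limit, where keeping the data is easy to defend, in the same way as a banned acid reducer, where it is not. If the tentative mechanism in Protocol 4.4 is right, an acid reducer taken before a fasted dose would act on the contrast that Cohort 3 is meant to estimate.

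Starting a prohibited drug should also lead to withdrawal. One sequence then falls under two intercurrent events with different strategies, and the SAP does not say which governs.

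At stake are the reported food effect, dose slope and dose-level summaries. These rest on about 12 participants in Cohort 3 and 6 active participants per dose level.

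**Working it through.** **Inputs from the documents.** Within-subject CV (CVw) 20% for AUC and 30% for Cmax, 12 evaluable participants and a 90% CI (SAP 8); 6 active participants per dose level (SAP 1.2).

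**Assumption.** The documents give neither the size nor the frequency of an interaction. One affected profile is taken to have its exposure multiplied by r = 0.7 or 0.5, a cut of 30% or 50%.

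1. **The plan's own precision.** SDw = sqrt(ln(1 + CVw²)) = 0.198 (AUC) and 0.294 (Cmax). Half-width h = t(0.95, n−1) × SDw × sqrt(2/n); precision = exp(h) − 1. At n = 12, h = 0.1452 gives 15.6% for AUC and h = 0.2152 gives 24.0% for Cmax. These round to the SAP's 16% and 24%.

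2. **Fed:fasted ratio, one of 12 fasted profiles affected.** Multiplier (1/r)^(1/12): 1.030 at r = 0.7 and 1.059 at r = 0.5. If the fed profile is affected instead, the multiplier is r^(1/12): 0.971 and 0.944.

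3. **Spread of the paired log difference.** Inflation = sqrt[(2·SDw² + (ln r)²/12) / (2·SDw²)].
   - AUC: 1.065 at r = 0.7 and 1.229 at r = 0.5.
   - Cmax: 1.030 and 1.110.

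4. **Two of 12 affected by a 2-fold change in the same direction.** The ratio is multiplied by 2^(2/12) = 1.122, or by 0.891. In a simulation of 40,000 trials with a true ratio of 1, coverage of the 90% CI stayed near 0.90 with one such profile. With two, it fell to about 0.82 (CVw 20%) or 0.85 (CVw 30%).

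5. **One of 6 at a dose level.** r^(1/6) = 0.942 and 0.891, so that level's geometric mean falls by 6% to 11%.

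6. **Dose slope, one 2-fold profile at an extreme dose.** Shift = ln(r)·(x − x̄)/Sxx, by ordinary least squares with 6 observations per dose, as an approximation to the mixed model. For four doubling dose levels (an assumption) the shift is 0.05 in size: ln 2 × 1.5 ln 2 / (30 (ln 2)²). For the eight illustrative doses in Protocol Table 4 it is 0.015 (top dose) to 0.026 (lowest dose).

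7. **Cost of setting affected data to missing.** With 11 participants instead of 12, precision goes from 15.6% to 16.5% (AUC) and from 24.0% to 25.5% (Cmax). With 10, it is 17.6% and 27.2%. In the simulation the expected ratio returned to 1.00, with coverage near 0.90.

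8. **The two strategies side by side.** The medication rule keeps observed data after intake. The discontinuation rule keeps data up to withdrawal and does not impute. For intake followed by withdrawal, both keep the observations made in between. They differ in the question they claim to answer, and no order of precedence is given.

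**The case against.** The strongest reply is that the event is rare and the protocol already contains it. Use before first dosing is an exclusion. Starting a prohibited drug is a withdrawal criterion, and no further doses follow. Medication is reviewed throughout each stay, and MAD participants are in-house from Day -1 to Day 8. In Cohort 3, the SAP's restriction to participants with both periods should remove someone withdrawn before the second active dose, though that wording is unclear for a four-period design. Most of this stands. What remains is chiefly SAD dosing after intake outside the unit between periods, and intake that comes to light only after dosing.

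The assumed 30% to 50% cut may also be too large for an acid reducer. Protocol 4.4 speaks of a marginal decrease with food. If an acid reducer acts only through that route, a cut of 10% to 20% in one of 12 fasted profiles is more in keeping, and the multiplier is (1/0.9)^(1/12) = 1.009 to (1/0.8)^(1/12) = 1.019. This is a fair limit for that mechanism, under which one profile would only move the ratio slightly towards 1. It does not limit an enzyme inducer.

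Four stronger readings are tempting, and the documents do not support them:
- **That the drugs are banned because they alter exposure.** The protocol never says so. Co-medication limits appear under liver risk and regular NSAID use under stomach risk (Protocol 2.3.1). An exposure reason is only implied, by the inducer window, the half-life rule and the remark on stomach pH.
- **That the SAP applies two opposite strategies.** In practice both keep the same observations; what is missing is precedence.
- **That one participant shifts a whole dose level.** It is one profile in six.
- **That the MAD regimen depends on this.** Protocol 9.2 names that as an aim of Cohort 3, and SAP 1.2 still leaves fed or fasted open. But Protocol 4.1 already sets MAD dosing as fed, and the dose escalation committee decides on accumulating data (4.6.3), not on the final SAP models.

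**Conclusion.** The concern holds in a limited form. The SAP states a rule that can bias the fed:fasted ratio, the dose slope and the dose-level means, its rationale does not fit those quantities, and nothing in the plan would show the effect. It should be changed, but it does not threaten the study.

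One affected profile moves the food-effect ratio by a factor of 1.03 to 1.06, well inside the planned AUC precision of 16%, and leaves CI coverage near nominal. It becomes material with several affected profiles or a strong interaction: two 2-fold profiles in the same direction shift the ratio by 11% to 12%.

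These sizes rest on assumed interactions of 30% to 50%, or 2-fold, in one or two participants. The documents support neither a size nor a frequency. That some prohibited drugs alter exposure to this compound is plausible from Protocol 4.4 and 6.5, but not established.

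**What to change.** In SAP 1.1.2 and 7.1 to 7.6, split the intercurrent event in two:

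- **(a) Permitted medication, and any medication judged blind to PK results not to affect absorption or metabolism:** treatment policy, as now.
- **(b) Prohibited medication judged able to affect absorption or metabolism:** hypothetical strategy. Set to missing the PK parameters from doses given after intake within the window the protocol already uses (7 days, 14 days for potential inducers, or 5 half-lives, whichever is longer).

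Make every classification blind to PK results and before database freeze. State that (b) takes precedence when discontinuation also occurs. Apply the rule explicitly to the food-effect analysis in 7.2, because 1.1.2 has no estimand for the fed:fasted contrast and 7.2.2.1 only refers back to it. Report the as-collected analysis as a sensitivity analysis.

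The cost is SAP text and the occasional loss of a profile: AUC precision of about 16.5% instead of 15.6% if one of 12 participants is lost. Safety analyses and clinical rules are unchanged.

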7.3. Statistical analysis for dose proportionality

7.3.1. Endpoints/Variables

Dose proportionality will be assessed following single doses of GSK3494245 separately for the fasted and fed cohorts during the Single Ascending Dose (SAD) via analyses of AUC (0-∞) and C_{max}. Only if required, the power model is fitted to dose normalized parameters to assess the dose proportionality for AUC (0-∞) and C_{max} (AUC(0-∞)_D and C_{max}_D).

7.3.2. Main analytical approach

Power model will also be fitted to assess dose proportionality as follows: $y = \alpha * \text{dose}^\beta$. In the log transformed manner this power model can be written as following

$$\log_e(Y) = \beta \times \log_e(\text{dose}) + \log_e(\alpha)$$

Where, y denotes the PK parameter being analyzed, dose denotes the dose administered to a subject. α depends upon random intercept subject effect and period effect and β is the coefficient of covariate $\log(\text{dose})$.

Log_e transformed data will be analyzed using a mixed effect model:

- Fixed effect: loge (dose), period
 - Random effect: Subject
- Data from all available doses will be considered. An unstructured covariance structure will be considered for the G matrix describing the between subject variability. If this model fails to converge, alternative covariance structures may be considered such as Variance Component, Compound Symmetry, etc. Akaike's Information Criteria (AIC) will be used to assist with the selection of covariance structure.
 - The Kenward and Roger method for approximating the denominator degrees of freedom and correcting for bias in the estimated variance-covariance of the fixed effects will be used.
 - Distributional assumptions underlying the model used for analysis will be examined by obtaining a normal probability plot of the residuals and a plot of the residuals versus the fitted values (i.e., checking the normality assumption and constant variance assumption of the model respectively) to gain confidence that the model assumptions are reasonable.
 - If there are any departures from the distributional assumptions, alternative transformations, such as data squared or square root of data, will be explored.

Model Results:

- The estimates mean slopes and 90% CIs of $\log_e(\text{dose})$ will be presented. Note that a slope ≈ 1 implies dose proportionality.

If the power model is failed to converge, analysis will be performed using Analysis of Variance (ANOVA) model to assess dose proportionality. The PK parameters (AUC (0- ∞), Cmax) will be dose-normalized first and multiplying by reference dose prior to loge-transformation, will be analyzed separately using mixed effects model.

- Fixed effect: loge (dose), period
- Random effect: Subject

The reference dose will be chosen based on the lowest clinically relevant dose over which PK can be adequately described.

- Data from all available doses will be considered. An unstructured covariance structure will be considered for the G matrix describing the between subject variability. If this model fails to converge, alternative covariance structures may be considered such as Variance Component, Compound Symmetry, etc. Akaike's Information Criteria (AIC) will be used to assist with the selection of covariance structure.
- The Kenward and Roger method for approximating the denominator degrees of freedom and correcting for bias in the estimated variance-covariance of the fixed effects will be used.

- Distributional assumptions underlying the model used for analysis will be examined by obtaining a normal probability plot of the residuals and a plot of the residuals versus the fitted values (i.e., checking the normality assumption and constant variance assumption of the model respectively) to gain confidence that the model assumptions are reasonable.
- If there are any departures from the distributional assumptions, alternative transformations, such as data squared or square root of data, will be explored.

Model Results:

Adjusted geometric means for each dose will be presented along with the standard errors (SE) and 90% CIs. Estimated treatment ratios to reference dose (First or lowest dose of each part) and corresponding 90% CI will also be presented.

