4.5. Justification for Dose

4.5.1. Human Predicted Pharmacokinetics

The preclinical pharmacokinetic (PK) data (mouse, rat and dog) was used to predict human blood PK parameters. Briefly, mouse, rat and dog in vitro and in vivo ADME datasets were employed to get the human PK estimates using various scaling approaches. The GlaxoSmithKline software package PK Predictor Pro (GUI v1.1.45 Calculation Engine v1.4.4) was used for IVIVE (in vitro-in vivo extrapolation), LBF (liver blood flow) and allometric scaling. GastroPlus 9.0 (Simulation Plus, inc.) was applied for the PBPK modelling [GlaxoSmithKline Document Number [2018N371507_02](#)]. NONMEM 7.4.3 (Icon Development Solutions) was used for PK simulations in human, based on GastroPlus parameters.

The different scaling methods predicted a clearance (CL) range of 3-11 mL/min/kg. Two clearance values were obtained based on the fact that the hepatocytes intrinsic clearance

in dog and human was shown to be saturated at increasing concentrations of the compound: a low clearance $CL=3.81$ mL/min/kg, and a high clearance $CL=6.67$ mL/min/kg. Both values were considered to predict human PK. The predicted steady state volume of distribution (VDSS) ranged from 0.7 to 2.2 L/kg with an average estimate of 1.28 L/kg, which was used to predict human PK. Taking into account only the liver extraction, human oral bioavailability is expected to be moderate (47 to 78%). Across the preclinical species (mouse, rat, beagle dog), a range of bioavailability values from 18 to 86% was observed. A value of 80% bioavailability was used for human PK prediction in the low clearance scenario, while a 64% bioavailability in the high clearance scenario [GlaxoSmithKline Document Number [2018N371507_02](#)].

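### Dose proportionality is read from one log-log slope, and per-dose estimates are modelled only if that model fails to converge, so a bend confined to the top doses can leave the slope compatible with 1

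*SAP*

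**What the plan says.** SAP 7.3.1 and 7.3.2 assess AUC(0-∞) and Cmax separately for fasted and fed cohorts. The log-transformed parameter is regressed on log dose with a random subject effect and the terms "Fixed effect: loge (dose), period". The reading rule is "Note that a slope ≈ 1 implies dose proportionality"; a 90% CI is shown and no acceptance limits are set.

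A second model is conditional: "If the power model is failed to converge, analysis will be performed using Analysis of Variance (ANOVA) model to assess dose proportionality". Only under that model does the SAP promise "Adjusted geometric means for each dose will be presented along with the standard errors (SE) and 90% CIs" and "Estimated treatment ratios to reference dose (First or lowest dose of each part) and corresponding 90% CI will also be presented". The fixed-effect line printed for this fallback is the same as for the power model, with log dose as a continuous term.

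The residual plots are described as checks of normality and constant variance. The stated response to a problem is a different transformation. SAP 7.3.1 allows the power model to be fitted to dose-normalised parameters if required. SAP 7.1 derives those parameters and summarises them descriptively. Protocol 9.5.2 has the power model alone, without a period term and without a fallback. No curvature term or lack-of-fit check appears in either document.

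**The concern.** The power model assumes the same exponent at every dose. If exposure is proportional at low doses and more than proportional only near the top, one slope averages the two parts and describes neither.

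The trigger for looking dose by dose is failure to converge. That is a numerical event: a straight line with a random intercept will normally converge on bent data. The other provisions do not fill the gap:

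- Refitting the power model to dose-normalised values only lowers the slope by exactly 1.
- A new transformation does not address a changing exponent.
- The descriptive dose-normalised summaries carry no model and no role in the conclusion.

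Dose proportionality after single doses is a stated secondary objective, and SAP 7.7 sends the MAD part to the same procedure. What is at stake is a report that calls exposure proportional when it is not at the highest doses studied.

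**Working it through.** **The plan's own precision figure.** SAP section 8 gives 36% for 6 participants and a between-participant CV of 30%. SD on the log scale = √ln(1 + 0.30²) = 0.294. Half-width = 2.571 × 0.294/√6 = 0.309, and exp(0.309) − 1 = 36%. This reproduces. The dose-proportionality section states no precision figure of its own.

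**Inputs for the illustration**

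- From the documents: Cohorts 1 and 2 with 8 participants each, 4 periods, 6 active per dose level, starting dose 20 mg, between-participant CV 30% (log SD 0.294), within-participant CV 20% for AUC (log SD 0.198). The 20% is stated for Cohort 3 and is assumed here for Cohorts 1 and 2.
- Assumed: a top dose of 400 mg, because doses are set during the study. Two spacings: uneven (20, 40, 80, 120, 160, 240, 320, 400 mg) and equal steps on the log scale. Cohort 3 fasted data are left out.
- Assumed bend: proportional up to 160 mg, local exponent 1.4 above. Excess at 400 mg = (400/160)^0.4 = 1.44, that is 44%.

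**Method.** Generalised least squares with a random subject intercept gives the expected slope b and its standard error. With z = (b − 1)/SE, the chance that the 90% CI includes 1 is Φ(1.645 − z) − Φ(−1.645 − z).

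| Spacing | Period term | b | SE | CI includes 1 |
|---|---|---|---|---|
| Uneven | no | 1.091 | 0.048 | 40% |
| Uneven | yes (SAP) | 1.002 | 0.085 | 90% |
| Log-equal | no | 1.128 | 0.052 | 20% |
| Log-equal | yes (SAP) | 1.086 | 0.092 | 76% |

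For the first row, z = 0.091/0.048 = 1.90 and Φ(1.645 − 1.90) = 0.40. The period term matters because each period of an ascending cohort is one dose level. Period is therefore partly confounded with dose and absorbs part of the bend.

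**A quadratic log-dose term, judged by its 90% CI, in the same setting.** It detects the bend in about 79 to 86% of trials without the period term and about 76 to 82% with it. At a within-participant CV of 30%, the documents' assumption for Cmax, the figure without period is about 50 to 58%.

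**Where masking does not occur.** For an assumed gradual 2.2-fold rise in AUC per mg centred near 200 mg, at CVw 20% and without the period term, the slope is about 1.19 to 1.22. Its CI excludes 1 in 98 to 99% of trials. The quadratic term detects that shape in only 45 to 60%.

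**Cohort 3a alone.** Each period is one dose level, so with a period term in the model the slope cannot be estimated, and neither can a quadratic or categorical dose effect.

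**The case against.** The strongest reply is that the planned slope works well for the most natural form of saturation. If clearance falls gradually over the range, the slope moves clearly above 1 and outperforms the quadratic term. That stands. It limits the concern to a bend confined to the top doses, and it is why per-dose estimates should be the main addition and the quadratic term only supportive.

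A reader might also infer that the protocol predicts a roughly two-fold bend. It does not:

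- Protocol 4.5.1 says hepatocyte intrinsic clearance "in dog and human was shown to be saturated at increasing concentrations of the compound", which is an in vitro finding.
- Tables 4 and 5 differ by (6.67/0.64)/(3.81/0.80) = 2.19 in AUC per mg, but they are alternative scenarios. Each is close to linear in dose, with fitted slopes of 0.997 and 0.999. They are not two ends of one curve.
- Table 6, projected from SAD data up to 160 mg, gives 1819/60 = 30.3 and 16955/480 = 35.3 per mg of daily dose, a 1.17-fold change.
- Protocol 4.4 mentions "high stomach solubility in the fasted acidic stomach that is not present in the fed state" to explain why food may lower exposure. It says nothing about dependence on dose.

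It is also fair that dose-normalised values will be visible in the descriptive tables, that residual-versus-fitted plots can show curvature whatever their stated purpose, that population PK is optional, and that the separate output specification may add displays. These could reveal a bend informally, but the SAP attaches no interpretation to it.

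Finally, this is an estimation-only secondary objective. Escalation is governed by committee review and the exposure limits in Protocol 4.6 and 7.1.1. The documents do not support reading this as a weakness in the protection of participants.

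**Conclusion.** The concern holds in a limited form. The SAP rests its conclusion on one slope and ties modelled per-dose estimates to an event unrelated to fit. With AUC at the top dose 44% above proportional, the slope's 90% CI would still include 1 in about 20 to 40% of trials without the period term and about 76 to 90% with it.

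Those figures rest on the assumed doses, the assumed bend shape and the CVs listed above. They cover two dose spacings and are not bounds. The documents do not establish that a bend exists, and saturation spread over the range would usually be seen, though not located. The reason to act is that the improvement is inexpensive and uses data already planned.

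**What to change.** In SAP 7.3.2, for each parameter and food state:

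1. Keep the power model. Regardless of its convergence, fit a second model to the log-transformed dose-normalised parameter with dose as a categorical fixed effect and subject random. The printed fixed-effect line has to change, because a log-dose term would force the per-dose means onto a line. Leave period out of this model, since in the ascending cohorts it cannot be separated from categorical dose unless a dose level recurs in another period.
2. Report geometric means by dose and ratios to one named reference dose, with 90% CIs, beside the slope.
3. For the fasted cohorts, add a quadratic log-dose term to the power model and report it with its 90% CI as a supportive lack-of-fit check.
4. State that the slope is interpreted together with items 2 and 3. Do not add a rule that picks a sub-range after seeing the data.
5. If Cohort 3a is analysed alone, omit period from its power model as well.

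The cost is SAP wording and one extra model per parameter and food state. Each quadratic test has about a 10% chance of flagging curvature that is absent; over two fasted parameters that is 1 − 0.9² = 19% if independent. Its power is lower at a within-participant CV of 30% and for gradual bends, so a null quadratic result should not be read as proof that the line fits.
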